2.7. Definition of Subgroups

Homogeneity of treatment safety and effects, both in hazard ratio (HR) and direction, will be assessed in the following subgroups classified at baseline:

- Stratification factor: Pancreatic (APC) or Non-Pancreatic (Non-APC)
- Age (18 - <65, 65- <75, \geq 75 years)
- Sex (Male, Female)
- Race (White, Black, Asian, Other, Unknown, Not Reported)
- Ethnicity (Hispanic or Latino, not Hispanic or Latino, Unknown, Not Reported)
- BMI (<25, 25-<30, 30-<35, \geq 35 kg/m²)
- Tumor type (Gastric/GE Junction, Lung, Lymphoma, Ovarian, and Other [which will include all the remaining non-pancreatic cancer types])
- Stage of Disease (I, II, III, IV) based on the TNM classification
- Baseline Khorana Score (2, 3, 4, and \geq 5)
- Baseline ECOG score (0-1, \geq 2)
- Geographic region (North America, Western Europe, Eastern Europe)
 - North America (USA, Canada), Western Europe (Belgium, France, Germany, Italy, UK), Eastern Europe (Bulgaria, Czech Republic, Russia), South America (Brazil)
- Baseline Creatinine Clearance (30 to < 50, 50 to <80, \geq 80 mL/min)

Race and ethnicity for subjects from France will be denoted as ‘Not Reported’ in the subgroup analysis as this information is not collected from France due to local regulations.

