5.2.4. Subgroup Analyses for the Primary Efficacy Composite Endpoint

Analyses of the primary efficacy composite endpoint will also be performed to examine the consistency of treatment effect across subgroups listed in Section 2.7. Homogeneity of treatment effect will be evaluated using the same model as described in Section 5.2.2 (stratified Cox proportional hazard model with treatment as a covariate). Subgroup analysis will be performed if there are at least 30 total randomized subjects in each subgroup category. Only descriptive

summaries will be presented for subgroups with fewer subjects. *The subgroup analysis by race and ethnicity will be denoted as 'Not Reported' for subjects from France as this information is not collected from the sites due to local regulation.*

The interaction of treatment with each of the subgroups will be analyzed based a stratified Cox proportional hazard model with stratification factor and treatment group with additional terms for subgroup and subgroup-by-treatment interaction. Further evaluations will be performed to assess and explain the nature of the interaction (qualitative or quantitative) if a significant (p value <0.10) interaction is observed. Significant interactions will be examined using a two-sided Gail-Simon⁸ test. Descriptive statistics (n, mean, standard deviation, median, and range) will be presented by treatment groups for each subgroup.

The subgroup analyses of the primary efficacy composite endpoint will be based on the '**Up-to-Day 180**' observation period for the ITT population with censoring as defined in Section 2.6.

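### The codes 'Unknown' and 'Not Reported' (the latter holding all French subjects) are levels of race and ethnicity and are not excluded from the interaction tests

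*SAP*

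**What the plan says.** SAP Section 2.7 lists the subgroup factors and their levels. Race is "Race (White, Black, Asian, Other, Unknown, Not Reported" and ethnicity is "Ethnicity (Hispanic or Latino, not Hispanic or Latino, Unknown, Not Reported". The section then sets a rule for one country: "Race and ethnicity for subjects from France will be denoted as ‘Not Reported’ in the subgroup analysis". The reason given is local regulation: French sites do not record either item. France also appears in the geographic region factor, inside "Western Europe (Belgium, France, Germany, Italy, UK".

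Section 5.2.4 repeats the French rule and specifies the test: "The interaction of treatment with each of the subgroups will be analyzed based a stratified Cox proportional hazard model", with terms for subgroup and subgroup by treatment. The nature of the interaction is examined further "if a significant (p value <0.10) interaction is observed", and significant interactions go to a two-sided Gail-Simon test. The only condition on levels is size: "Subgroup analysis will be performed if there are at least 30 total randomized subjects in each subgroup category". Smaller subgroups are summarized descriptively.

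Neither section removes 'Unknown' or 'Not Reported' from the interaction term or from the Gail-Simon test.

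**The concern.** 'Unknown' and 'Not Reported' record that a value is absent. They are not races or ethnicities, and 'Not Reported' contains a whole country by rule. Making them levels of the factor can have three effects.

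- **Country read as race.** If the treatment effect differs in France, the difference enters the race and ethnicity interaction tests through the 'Not Reported' level.
- **Diluted tests.** Each code adds one degree of freedom. Unless the effect differs in that level, the extra degree of freedom adds no signal and lowers the power to detect a difference between the real groups.
- **An ambiguous size rule.** Read level by level, the rule can move a small real group to descriptive summary while a larger 'Not Reported' level stays in the test. Read strictly, with every category needing 30 subjects, a handful of 'Unknown' subjects could remove the factor from testing altogether.

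What is at stake is the interpretation of two subgroup tests. The primary and key secondary results do not depend on it.

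**Working it through.** **Inputs from the SAP.** Race has 6 levels, of which 4 are substantive. Ethnicity has 4, of which 2 are substantive (2.7). The interaction level is 0.10 and the minimum category size 30 (5.2.4). Section 1.4 gives event rates of 14.5% and 6.0%, about 700 subjects later raised to about 800, and 20% dropout.

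**The plan's own figure.** The SAP states no power for any interaction test. Its stated power is >90% for the primary endpoint. With 350 × 0.8 = 280 per group and a pooled rate of 0.1025:
- Null SE = √(2 × 0.1025 × 0.8975 / 280) = 0.0256
- Alternative SE = √((0.145 × 0.855 + 0.06 × 0.94) / 280) = 0.0254
- Power = Φ((0.085 − 1.96 × 0.0256) / 0.0254) = Φ(1.37) = 91.5%

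This agrees with the SAP, so the design inputs can be used below.

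**Degrees of freedom.** An interaction test on k levels has k − 1 df.

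| Factor | Both codes excluded | One code kept | Both kept |
|---|---|---|---|
| Race | 3 | 4 | 5 |
| Ethnicity | 1 | 2 | 3 |

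**When a code enters.** It needs 30 subjects: 30/700 = 4.3%, or 30/800 = 3.8%.

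**Power lost to the extra df.** Power = P(noncentral χ² with k − 1 df > critical value at 0.10). The critical values for 1 to 5 df are 2.71, 4.61, 6.25, 7.78 and 9.24. Assume 80% power without the codes and no true heterogeneity in them, so that the noncentrality stays fixed. The race column also needs all four substantive groups to be in the test.

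| | Noncentrality | No code | One code | Two codes |
|---|---|---|---|---|
| Ethnicity | 6.18 | 80% (1 df) | 71% (2 df) | 65% (3 df) |
| Race | 8.80 | 80% (3 df) | 76% (4 df) | 73% (5 df) |

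**Is 80% realistic?** Take exponential event hazards of −ln 0.855 = 0.157 and −ln 0.94 = 0.062 over six months, and a dropout hazard of −ln 0.8 = 0.223. The expected events are 350 × (0.130 + 0.054) ≈ 64. With information per level of events × share / 4, the noncentrality for one group against the rest is (64.5/4) × (known share) × p(1 − p) × (difference in log HR)². Assume a very large contrast, HR 0.4 in the majority and 1.6 in the others. Let the others be p = 20% (race) or 15% (ethnicity) of subjects with known values, France 5–20% and 'Unknown' 4% of all subjects. With both codes excluded, power is 46–53% for race and 54–60% for ethnicity. With both kept, it is 39–45% for each.

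**Country effect.** Assume HR 0.4 in every real group, HR 1.0 in 'Not Reported', 64.5 events, and a share s of subjects in that level. The noncentrality is (64.5/4) × s(1 − s) × (ln 2.5)², with (ln 2.5)² = 0.840.

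| Share s | Noncentrality | Race, 4 df | Ethnicity, 2 df |
|---|---|---|---|
| 5% | 0.64 | 15% | 18% |
| 10% | 1.22 | 20% | 24% |
| 20% | 2.16 | 28% | 35% |

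These are rejection rates with no race or ethnicity heterogeneity at all. With the code excluded they return to the nominal 10%.

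The shares and hazard ratios are assumptions, and the approximation is a large-sample one applied to levels with few events.

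**The case against.** The strongest reply is that the effect may be nil. The 30-subject rule can drop a small code by itself, and on the strict reading a small race group could mean that no race test is run. The SAP gives no count for France or for 'Unknown'. This stands: the consequence is conditional. A reader might infer that the tests will in fact measure country and lose power, but the document does not support that.

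A reader might also infer that France could produce a qualitative race interaction. That is unlikely at the size threshold. Thirty subjects at the planned rates give 30 × (0.145 + 0.06)/2 ≈ 3 events, so the SE of the log HR is about 2/√3 = 1.15. Even at Gail-Simon's lowest bar (two groups, 0.10 level, critical value 1.64, so |z| > 1.28), the HR in that level would have to exceed about exp(1.28 × 1.15) ≈ 4.4.

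Other points also carry weight. The SAP discloses the French rule twice, rows would carry the label 'Not Reported', and 5.2.4 requires a significant interaction to be explained, so a careful reader might trace the cause. The Data Presentation Specifications, not shown, may deal with missing-value rows. Race and ethnicity are two of twelve factors, and their tests lie outside the testing hierarchy of Section 5.5.

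What remains is that the SAP expressly makes these codes levels and then tests every factor. A size filter is not a rule for missing data, because it keeps any code that reaches 30.

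**Conclusion.** The point holds as a minor one. The SAP defines missing-data codes as race and ethnicity levels and does not exclude them from the interaction or Gail-Simon tests. If a code reaches 30 subjects, the tests are diluted and a French effect can appear as a race or ethnicity interaction. On the strict reading of the size rule, a sparse code could cancel the factor's analysis.

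The falls from 80% to 71% and 65% (ethnicity) and to 76% and 73% (race) illustrate the cost of added degrees of freedom from an assumed starting power. A reader might take them as this trial's expected loss. They are not: the SAP states no interaction power, and about 64 expected events suggest it is well below 80%. The 15–28% (race) and 18–35% (ethnicity) rejection rates likewise require the treatment effect to be absent in 'Not Reported' and that level to hold 5–20% of subjects. Primary and key secondary inference is untouched.

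**What to change.** Add one sentence to Section 5.2.4: 'Unknown' and 'Not Reported' are shown as descriptive rows only, and are excluded from the race and ethnicity interaction tests, from the Gail-Simon test for these factors, and from the 30-subject minimum-size rule. Settling this before database lock avoids choosing the levels after the data are seen.

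The cost is small. These subjects leave two exploratory tests and stay in every other analysis. One limit should be acknowledged: the region factor does not isolate France, because it pools France with Belgium, Germany, Italy and the UK. A French effect would therefore be examined only within Western Europe.

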3. INTERIM ANALYSIS AND INDEPENDENT DATA MONITORING COMMITTEE (IDMC)

No interim efficacy analysis is planned in this study and there are no pre-specified stopping rules planned in this study. However, an IDMC has been set up for this study to periodically assess the safety of subjects in this study and to evaluate the efficacy data as necessary to ensure that the safety of subjects is not compromised. Details of the IDMC roles, responsibilities, and key activities/timelines are provided in the IDMC charter.

The programming rules for deriving the analysis variables and the data tables for the IDMC meetings are specified in the data presentation specification document (DPS). Brief description is included in the Attachment.

4. SUBJECT INFORMATION

4.1. Demographics and Baseline Characteristics

Summaries of demographic and baseline characteristics, risk factors and medical history will also be provided by treatment group.

Descriptive statistics (such as mean, standard deviation, median, minimum and maximum) will be provided for continuous variables such as age (at baseline visit), weight, and height. Counts and (appropriate) percentages will be provided for categorical variables such as sex and race.

4.2. Disposition Information

The number of subjects included in the analysis populations (ITT, PP and safety) and number of subjects who completed or withdrew from the double-blind period will be summarized by treatment group and stratification factor: APC or non-APC.

Summaries of reasons for withdrawal from the double-blind period and permanent discontinuation of treatment will be provided by treatment group.

Time to study drug discontinuation will be summarized by treatment group using the Kaplan-Meier method.

Time to early study discontinuation will also be summarized by treatment group using the Kaplan-Meier method.

4.3. Treatment Compliance Based on Exposure

The following rules will be implemented to determine the compliance based on exposure information.

For subjects who died during the double-blind period and for those subjects who permanently discontinued their treatment early the compliance will be determined as:

Days on drug= [(last dose date-first dose date+1) – days of drug interruption]
Total exposure duration = last dose date-first dose date+1

Compliance (%) = [Days on drug/Total exposure duration]x100

For all other subjects who completed or withdrew (but had not ended treatment early) from double-blind period the compliance will be determined as:

Days on drug= [(last dose date-first dose date+1) – days of drug interruption]
Total exposure duration = double-blind end date-first dose date+1

Compliance (%) = [Days on drug/Total exposure duration]x100

4.4. Extent of Exposure

Duration of double-blind treatment is defined as the duration between the first dose date and last dose date, inclusive. Duration of treatment exposure will be summarized by treatment group.

Total treatment duration = last dose date - first dose date + 1.

The total number of temporary drug interruptions (>3 days) and reasons for interruptions will also be summarized by treatment group.

Duration of double-blind period will also be summarized. The duration of double-blind period is defined as the duration from randomization up to the double-blind period end date.

Duration of Double-Blind period = Double-blind period end date (completers or withdrew subjects) – randomization date + 1.

4.5. Systemic Cancer Therapies and Concomitant Medications

Systemic cancer therapies at randomization and during the double-blind period (those that started after randomization and those started before randomization by continued during the double-blind period) will be summarized by treatment group. The number and percentage of randomized subjects, who received systemic cancer therapies will be presented.

Concomitant medications include all medications received at or after the randomization date. These will be summarized by treatment group, for all randomized subjects, using the Anatomical Therapeutic Chemical (ATC) dictionary.

4.6. Study Drug Discontinuation and Early Withdrawal from Double-Blind Period

If a subject's study treatment must be permanently discontinued before the end of the double-blind treatment period, this will not result in automatic withdrawal of the subject from the study and they are encouraged to continue to be followed for efficacy and safety outcome until the end of the double-blind period/Day 180. Data from remaining scheduled visits are collected until the subject either completes the double-blind period/Day 180 visit or withdraws early from the study.

Outcome data for all subjects, those who completed the double-blind period as well as those who withdrew early from the double-blind period is also collected at the Day 210/EOS visit as agreed during the informed consent. Every effort will be made to follow-up the subject and collect the data including vital status. In the event a subject withdrew consent or is lost-to-follow up, the vital status data (dead/alive) will be obtained through public information (death and other registries) per local guidelines and as allowed by local registration.

Thus, there are two scenarios as described below:

1. Subject permanently discontinues study treatment but completes the double-blind period (i.e. completed the study/end of double-blind period)
 - a. If subject experiences an efficacy (primary or secondary) endpoint event at any time during the study (from randomization through double-blind period completion), then the event and corresponding time to the occurrence of the event will be included in the analysis of primary efficacy composite endpoint
 - b. If a subject has no efficacy composite endpoint event (primary or secondary) during the time in study, then this subject will be censored with the time to censoring defined as the time from randomization to last day of their complete assessment for study outcomes during the double-blind period [double-blind completion].
2. Subject permanently discontinues study treatment and withdraws early prior to the end of the double-blind period (i.e. withdrew from the study altogether) or dies during the double-blind period
 - a. If subject experiences an efficacy composite endpoint event (primary or secondary, including VTE-related deaths) after withdrawing from the study and the time to the occurrence of the event is prior to Day 180, then this event and corresponding time to the occurrence of the event will be included in the analysis of primary efficacy composite endpoint. If subject dies (all causes other than VTE-related) after withdrawing from the study and reported on Day 210 but event time is prior to Day 180, then this event and corresponding time to death will be included in the all-cause mortality endpoint analysis
 - b. If a subject does not experience any efficacy composite endpoint event (primary or secondary) in the study, then this subject will be censored. The time to censoring is defined as the time from randomization to the minimum of (last day of their complete assessment for study outcomes during the double-blind period/Day 180 [double-blind withdrawal date for those who withdrew], or death date [censored at death date for analysis not related to the specific death endpoint]).

5. EFFICACY

5.1. Analysis Specifications

5.1.1. Level of Significance

All statistical tests will be 2-sided and conducted at 5% significance level unless specified otherwise.

The fixed-sequence step down procedure with a priori ordered hypotheses will be used to control the type I error for multiple testing (Section 5.5). If the result of a test in the sequence is not significant, the tests in lower hierarchical order will be interpreted as not significant regardless of the actual p-value. All confidence intervals will be estimated at the 95% level.

5.1.2. Data Handling Rules

The primary efficacy and key secondary endpoint analyses in this study will be based on the ITT analysis population (which includes all randomized subjects). All safety endpoints will be analyzed based on the safety analysis population (which includes all randomized subjects who receive at least one dose of study drug).

Time to event analyses will use censoring rules that apply to subjects with no primary efficacy outcomes during the specified observation periods, or, to subjects who withdrew from the study, or to subjects who die because of reasons other than VTE-related or bleeding, or withdrew informed consent before the end of the predefined treatment duration (Section 2.6 describes in detail all the censoring rules for the different observation periods).

All efforts will be made to collect complete data for all subjects randomized in this study to avoid missing or partial event dates. If the event date is not known, the investigators will provide their best estimate as to when the event occurred based on all the data available for that subject. In the extreme scenario where the event date is partial (missing day and month and year available), the day will be imputed as the first of the month.

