2.5. Definition of Study Dates and Observation Period End Dates

The study dates and period end dates will be used to define the time period for data included in the analysis of efficacy and safety endpoints for the different observation periods (defined in Section 2.6).

Study Day 1 date: the date of randomization of the subject.

End-of-Study (EOS): the date of the last study-related procedure for the subject (EOS is defined as last assessment day during the study, including the Day 210/Post-Treatment Follow Up visit) and is defined as the minimum (last assessment day during the study, death date).

Double-Blind period start date will be the date of randomization.

Double-Blind period end date will be defined as the completion/early withdrawal date (date of completion or early withdrawal [any reason including death] from the double-blind period).

Up-to-Day 180 observation period end date will be defined as follows;

- Day 180/EODB completion date (for subjects who completed the double-blind period) or
- Death date (subjects who died during the double-blind period [DB reason=death] or during any time from randomization through Day 180 [died post withdrawal from DB but before Day 180/EODB visit] or
- Maximum (double-blind withdrawal date, randomization date + 180 days) for subjects who withdrew early from the double-blind period [any reason other than death] and had not died during the time from randomization through Day 180

First dose date: the date on which the first dose of study drug is taken by the subject. If missing or partial for a subject who takes study drug, the first dose date is set to the randomization date.

Last dose date: the date on which the last dose of study drug is taken by the subject (dose end date). If the dose end date is missing or partial for a subject who takes study drug, the last dose date is set as follows

- Maximum (Minimum (discontinuation date in the double-blind period [including death date during double-blind period], last visit date when drug is dispensed + number of pills dispensed - number of pills returned at following visit), imputed partial last dose date, exposure start date of last record))
 - Imputation rule for partial dates: If only the day is missing, then day imputed to the last day of that month. If day and month are missing, the date will be imputed to the start date if year is the same, else imputed to January 1st.

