2.6.1. Up-to-Day-180 Observation Period

This observation period includes data from randomization to Up-to-Day 180 end date (defined in Section 2.5).

Event: All efficacy events (with respect to deaths, *VTE-related deaths are counted as events for primary efficacy endpoint. For the secondary efficacy endpoints, all-cause deaths are counted as events*) that occurred from randomization through the Up-to-Day 180 end date (Section 2.5) will be included in the analysis of this observation period.

- Event time - The time to event is defined as the time from randomization to the time of the first event during this observation period.

Censoring: Subjects who did not experience an event during this observation period will be censored at the last day of their complete assessment for study outcomes.

Subjects who died during this observation period will be censored as of their death date for endpoint analyses not related to death.

- Censoring time - The time to censoring is defined as the time from randomization to the minimum of (last day of their complete assessment for study outcomes during the double-blind period [double-blind completion/withdrawal], death date [non VTE-related deaths for primary efficacy composite endpoint]).

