2.6.2. On-Treatment Observation Period

This observation period includes data from the day of the **first dose of study drug to 2 days after the last dose of the study drug, inclusively** (dose dates defined in Section 2.5).

All randomized subjects will be included in the On-Treatment observation period. A conservative approach will be used for subjects who were randomized but never dosed to include any event that may occur even if the subject did not take study drug. This is defined to include VTE-related events that occur during the study even if the subject had not taken study drug. Only those events that occur prior to the double-blind period end date will be included in the on-treatment observation period.

Event: All efficacy and safety events (with respect to deaths, *VTE-related deaths are counted as events for primary efficacy composite endpoint. For Bleeding related deaths, major bleeding is counted as events for the primary safety endpoint*) that occurred from the date of first dose of study drug up to the last dose of study drug+2 days will be included in the analysis of the On-Treatment observation period.

- Event time - The time to event is defined as the time from first dose date to the time of the first event during this observation period.
 - For randomized subjects but never dosed: The time to event will be defined as the time from randomization to the time of the event during the time in study. This imputation rule will be applied only for the ITT population.

Censoring: Subjects who do not experience an event during this observation period will be censored.

Subjects who died during this observation period will be censored as of their death date for endpoint analysis not related to death.

- Censoring time - The time to censoring is defined as the time from first dose date to the minimum (earliest) of (last dose date+2 days, death date).
 - For randomized subjects but never dosed the time to censoring will be defined as the time from randomization to the minimum of (last day of their complete assessment for study outcomes during the double-blind period [double-blind completion/withdrawal], death date [non VTE-related deaths for primary efficacy composite endpoint]).

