6.1.1. Bleeding Events Classification

Like efficacy outcomes, the same independent CEC will adjudicate and classify bleeding events per the definitions in the CEC Charter.

Bleeding events will be classified as major, clinically relevant non-major, or minor bleeding using the ISTH classification as follows:

Major Bleeding

Major bleeding is defined as clinically overt bleeding that is associated with:

- A reduction in hemoglobin of 2 g/dL or more, or
- A transfusion of 2 or more units of packed red blood cells or whole blood, or
- Occurrence at a critical site defined as intracranial, intra-spinal, intraocular, pericardial, intra-articular, intra-muscular with compartment syndrome, retroperitoneal, or
- Fatal outcome

Clinically Relevant Non-Major Bleeding

Clinically relevant non-major bleeding defined as overt bleeding not meeting the criteria for major bleeding but associated with:

- Medical intervention
- Unscheduled contact (visit or telephone call) with a physician
- Temporary cessation of study treatment, or
- Discomfort such as pain, or impairment of activities of daily life

Minor Bleeding

All other overt bleeding episodes not meeting the criteria for major or clinically relevant non-major bleeding will be classified as minor bleeding (corresponds to minimal bleeding event captured on the case record form).

Imputation Rules for Partial Bleeding Start Dates

If the bleeding start date is a partial date (only unknown day)

- If only the day is missing, and the month and year are known, the month and year of the AE will be compared with the month and year of double-blind medication start date.
 - If the both the month and year of the bleeding event is equal to the month and year of double-blind medication start date, then the imputed day will be the start day of medication.
 - If the month or the year of the bleeding event is different, then the imputed day will be the 1st day of the month.

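### The rule for partial efficacy event dates has no floor at randomization, so an event in the randomization month can get a negative event time

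*SAP*

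**What the plan says.** SAP Section 5.1.2 deals with incomplete efficacy event dates in two steps. If the date is unknown, "the investigators will provide their best estimate as to when the event occurred based on all the data available for that subject". A fallback covers what remains, and it opens with "In the extreme scenario where the event date is partial (missing day and month and year available"). Its instruction for such a date is that "the day will be imputed as the first of the month". No lower bound is attached.

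The primary analysis starts at randomization. Section 2.6.1 says of the window: "This observation period includes data from randomization to Up-to-Day 180 end date (defined in Section 2.5"). Of the event time it says: "The time to event is defined as the time from randomization to the time of the first event during this observation period". Section 2.5 fixes the origin: "Study Day 1 date: the date of randomization of the subject". The On-Treatment period instead takes events "that occurred from the date of first dose of study drug up to the last dose of study drug+2 days" (Section 2.6.2), and the Post-First Dose period (Section 2.6.4) also starts at first dose.

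Other date rules in the SAP do have a floor. For a bleeding date whose month and year match the start of medication, "then the imputed day will be the start day of medication" (Section 6.1.1). Section 6.2.1 does the same for adverse event onset, and Section 2.5 does not let the last dose date fall before the first dose date.

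**The concern.** The first of the month is a sensible default only when the subject was already in the study on that day. In the month of randomization that is true only for subjects randomized on the 1st. For anyone else the rule produces an event date earlier than the time origin.

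The primary analysis would then receive a confirmed event with a negative time. Someone would have to decide how to handle it, and the SAP gives no instruction. A pre-specified rule for the primary endpoint should not depend on an unwritten correction, particularly one that might be needed after unblinding.

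The rule can also treat parts of one endpoint differently. Composite endpoint #4 (Section 5.6.1) combines symptomatic VTE with major bleeding. If each component follows its own date rule, a bleed and a VTE with the same partial date in the month of randomization and first dose are placed differently: the bleed on the medication start day, the VTE before randomization.

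**Working it through.** The SAP states no figure on this point, so there is none to reproduce. The check is date arithmetic, followed by a rough estimate of size.

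**1. Event time under the rule.** Let r be the calendar day of randomization, and let the event fall in the same month with its day missing.

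- Imputed time = (1st of month) − (randomization date) = 1 − r days.
- r = 1 gives 0. r = 2 gives −1. r = 30 gives −29.
- In a 30-day month the time is negative for 29 of the 30 possible randomization days.

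For the periods that start at first dose, replace r by the calendar day of first dose.

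**2. Example.** A subject is randomized on the 20th and the true event is on the 28th of the same month.

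| Date used | Time from randomization |
|---|---|
| True date | 28 − 20 = +8 days |
| Section 5.1.2 rule | 1 − 20 = −19 days |
| Floor at randomization | 20 − 20 = 0 days (Study Day 1) |

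**3. Comparison with the SAP's other date rules.**

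| Date | Section | Floor stated |
|---|---|---|
| Efficacy event | 5.1.2 | None |
| Bleeding start | 6.1.1 | Medication start day, if month and year match |
| Adverse event onset | 6.2.1 | Medication start day, if month and year match |
| Last dose | 2.5 | First dose date |

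No other section supplies a floor for efficacy event dates.

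**4. Size.** Two assumptions are needed that are not in the SAP: event times uniform over 180 days, and randomization equally likely on each day of a 30-day month.

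- Share of events in the randomization month, leaving out subjects randomized on the 1st: the sum of (30 − r) for r = 2 to 30 is 406, and 406 / (30 × 180) = 7.5%. A day-by-day count over one calendar year gives 7.6%.
- Planned events from the Section 1.4 rates (14.5% and 6.0%): 350 × (0.145 + 0.060) = 71.75. If the 20% who discontinue contribute no events, 280 × 0.205 = 57.4. With 800 randomized, 400 × 0.205 = 82.
- Events in the randomization month: 57.4 × 0.075 = 4.3, up to 82 × 0.075 = 6.2.
- The SAP does not give the share of these with a missing day. Assuming 1% to 5%, the expected number affected runs from 4.3 × 0.01 = 0.04 to 6.2 × 0.05 = 0.31.
- Treating the count as Poisson, the chance that no event is affected is exp(−0.31) = 73% to exp(−0.04) = 96%.

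**The case against.** The other side has four arguments.

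- **The trigger is remote.** Section 5.1.2 asks for every effort to obtain complete dates, then for an investigator's estimate, and calls what remains an extreme case. Primary events are objectively confirmed and adjudicated (Sections 5.2 and 5.2.1), so a DVT or PE will normally carry a dated test. This stands and keeps the point minor.

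- **The 7.5% is probably too high.** Ultrasound is scheduled every 8 weeks (Section 1.2), so asymptomatic proximal DVT will mostly be found around Week 8 or later, apart from scans done at early discontinuation of study drug. VTE on the screening scan is an exclusion criterion (Section 2.4.2). This also stands. The figure is best read as a rough guide that leans high.

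- **Loss of the event does not follow.** Section 2.6.1 includes events according to when they occurred. An event known to have happened after randomization could be kept, with only its time invalid, and a negative time would be easy to spot. A reader might infer that the event is necessarily dropped, or that the subject leaves the ITT analysis. The SAP does not say so: Section 2.4.1 keeps every randomized subject in the ITT population, and nothing in the document describes how software would treat such a record. Exclusion is one literal reading and no more. The invalid time arises on either reading.

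- **A floor may be written elsewhere.** Section 1 leaves programming instructions to the Data Presentation Specifications, which are not at hand. That cannot be checked. The SAP does state the imputation rule itself, however, and as stated the rule is incomplete. It also states the floor for its safety dates.

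**Conclusion.** The point holds as a minor defect. As written, Section 5.1.2 yields a negative event time for a partial-date event in the month of randomization, unless randomization fell on the 1st. It is also out of line with the SAP's bleeding, adverse event and last dose rules. This conclusion follows from the dates alone and needs no assumption.

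The size does rest on assumptions: a constant event rate, randomization spread evenly over the month, and a missing-day share of 1% to 5%. On these the expected number of affected events is about 0.04 to 0.31. None is the most likely count, one is possible, and the primary conclusion is unlikely to change. A reader might infer that about 8% of primary events are at risk, or that the result could turn on this rule. The SAP does not support that, because only events that also still lack a day after the investigator's estimate are affected.

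**What to change.** Replace the last sentence of the partial-date rule in Section 5.1.2 with wording such as:

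> If the month and year of the event equal those of randomization, the imputed date is the randomization date; otherwise it is the first of the month. For the On-Treatment and Post-First Dose periods, if the month and year equal those of the first dose, the first dose date is used for dosed subjects, and the randomization date rule applies to never-dosed subjects.

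The last clause is needed because Sections 2.6.2 and 2.6.4 include randomized subjects who were never dosed, time them from randomization, and have no first dose date for them. Making the floor conditional on the same month follows the pattern of Section 6.1.1 and avoids pulling an event from an earlier month into the window. No upper limit is needed: the later of the 1st and the time origin cannot fall after the true date of an event that occurred on or after that origin.

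The cost is two sentences in the SAP and a small change to the date derivation, made before database lock. No data collection or sample size is affected.
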